**IRB#: 09-060 A(4)**

However, we will descriptively assess any differences in results between the two sets of analysis as much as the data permits if this situation arises.

Secondary Aim #1: To attempt to corroborate voxel-based parameter estimates reflecting tumor cell proliferation with estimates derived using standard ROI-based pharmacokinetic modeling methods, for improving the characterization of high-grade gliomas using dynamic  $^{18}\text{F}$ -FLT PET-CT.

Statistical Methodology for Secondary Aim #1: To corroborate the voxel-based method with the ROI-based approach, pharmacokinetic modeling will be assessed by comparing the estimated parameter values for the entire intra-tumor ROIs to the average of the voxel-by-voxel parameter values among the voxels comprising the same ROIs. This analysis will focus on the  $k_3$  value. For each ROI, we would like to see the estimated  $k_3$  value derived from the entire ROI to be within 25% of the average  $k_3$  value determined for the multiple voxels. The ratio of two  $k_3$  values will be computed for this purpose. As an additional analysis, we will calculate the concordance correlation coefficient (CCC) to evaluate the agreement between the ROI-based and the average voxel-based parameter values. A modified version of the CCC that allows for clustered data will adjust for the fact that there may be multiple observations per patient contributing to the estimates.

Secondary Aim #2: To assess whether static measures of  $^{18}\text{F}$ -FLT uptake can adequately serve as non-invasive biomarkers of proliferative activity or whether parametric images, based on compartmental analyses of the FLT pharmacokinetics, are required by correlating findings of both approaches with regional histologic assays of tumor cell proliferation.

Statistical Methodology for Secondary Aim #2: Using the same methods described for the primary arm, the relationship between Ki67 and the static measure of  $^{18}\text{F}$ -FLT (the SUV), and the parametric measure ( $k_3$ ) will be explored. The strength of the relationship between these two parameters and Ki67 will be compared descriptively.

Exploratory Aim: To evaluate whether differences in gene expression seen between areas of increased and decreased proliferative activity on parametric maps define consistent differential transcriptome signatures for comparison with known molecular subclasses of GBM and known pathways.

Statistical Methodology for Exploratory Aim:

ACGH: Array CGH data will be analyzed through the software pipeline developed within MSKCC's Cancer Genome Characterization Center within The Cancer Genome Atlas Project. This includes extensive QC annotation, normalization and artifact reduction, and segmentation analysis.

Expression analysis for gene signatures: Expression array data will be normalized by RMA and differential expression of paired samples determined by Significance Analysis of Microarrays (SAM). Methods of analysis cross-sample will aim at determining core signature genes which are commonly differentially expressed in relation to imaging features. These methods will depend on the

**Memorial Sloan-Kettering Cancer Center  
IRB Protocol**

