Tailoring targeted therapies based on an individual tumor's unique molecular and biochemical signatures is an ultimate goal in managing brain tumor patients. Characterizing tumors at multiple sites, guided by heterogeneous metabolic/functional imaging findings, may capture variation in potential tissue biomarkers, such as EGFR amplification or MGMT methylation, which are frequently heterogeneously distributed. To meet this challenge, it will be necessary to determine clinically useful biomarkers with prognostic and predictive value to improve selection of specific therapeutics and to assess early response/progression for modifying treatment protocols. High throughput molecular analyses of surgically procured tissue have enhanced the characterization of gliomas, resulting in the definition of novel tumor sub-classes, better diagnostic accuracy, and improved prognostication. Prolonged progression-free and overall survival in glioblastoma patients treated with DNA alkylating agents, for instance, has been linked to MGMT hypermethylation in the majority of tumors. The results of such studies have suggested that gene expression profiling will impact future clinical practice in terms of cancer diagnosis, prognosis, and choice of optimal treatment. Under certain conditions, however, such as during the course of treatment, brain tumor biopsy may be impractical, and given that radiographic disease progression is often associated with morbid decline, there is a critical need to establish early and reliable non-invasive biomarkers of treatment response.

This study will also lay the groundwork for establishing the interpretability of  $^{18}\text{F}$ -FLT heterogeneity within and across tumors on a voxel-wise basis. The feasibility of voxel-wise estimation of proliferation will be established, and validated against traditional ROI-based pharmacokinetic approaches. The results of these studies may inform the design of larger prospective studies assessing  $^{18}\text{F}$ -FLT proliferative response in trial of targeted therapies, as well as determine the potential for FLT-PET to serve as a biomarker for proliferation at the tissue level. An FDA-approved IND has been issued for  $^{18}\text{F}$ -FLT (#104742) at this institution.

Memorial Sloan-Kettering Cancer Center  
IRB Protocol

IRB#: 09-060 A(4)

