
Primary Aim Study Design: Preoperative anatomical MRI images will be uploaded to the BrainLAB VectorVision® neuronavigation system, a frameless stereotaxy and image-guided surgical navigation system integrated with the Intraoperative MRI suite. Planned resection volume will be contoured by the neurosurgeon conventionally, based on the anatomic MRI.  $^{18}\text{F}$ -FLT PET-MRI studies will then be uploaded and registered by a radiologist. For each patient undergoing resection, up to four prescribed ROIs within the planned resection volume will be selected for potential targeted biopsy based on concordance/discordance or heterogeneity of PET and MRI imaging characteristics (i.e., increased  $^{18}\text{F}$ -FLT uptake/MRI-enhancing; increased  $^{18}\text{F}$ -FLT uptake/MRI-non-enhancing; low  $^{18}\text{F}$ -FLT uptake/MRI-enhancing; increased  $^{18}\text{F}$ -FLT uptake/MRI-nonenhancing). ROIs will be no smaller than a cubic centimeter. The operative plan, in terms of the tumor resection volume, will not be guided by decisions regarding sites of potential biopsy selected on the co-registered FLT PET-MRI study. It is expected that

IRB  
PB

Amended: 12/27/11

**Memorial Sloan-Kettering Cancer Center  
IRB Protocol**

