**Amended: 12/27/11**

Memorial Sloan-Kettering Cancer Center  
IRB Protocol

IRB#: 09-060 A(4)

microvessel density (CD31) will be applied to FFPE sections. Serial sections will be reviewed by an experienced neuropathologist. Ki-67 staining will be evaluated and a score designated indicating the percentage of positively stained tumor cells per quartile of tumor tissue. All cells with nuclei staining of any intensity will be defined as positive. The proliferative activity score, quantified as the percentage of MIB-1 stained nuclei per total nuclei in the sample, will be estimated from a representative slide selected by the neuropathologist. For MVD assessment using CD31, tumor sections will be scanned at low magnification (x40) to identify the region of the section with the highest microvessel density. This area will be counted at a magnification of x200 for CD31-positive expression, and the proportion of CD31-positive cells computed for all specimens.

Histologic findings at a given biopsy site will be compared with ROI analyses at the same location on the co-registered PET-MRI studies. Pharmacokinetic modeling will be applied to these ROI measurements in order to generate parametric maps reflecting the proliferation rate constant,  $k_3$ , and  $K_{trans}$  (microvascular permeability). Estimated parameter values will be correlated with the presence of molecular markers (MIB-1, CD31), and compared with imaging features at the prospectively defined biopsy sites.

Secondary Aim #1 Study Design: The objective will be to investigate the feasibility of applying a novel imaging software platform to the measured dynamic brain PET imaging data. Voxel-based parameter estimates will be generated using ROIs selected for targeted biopsy and, in turn, utilized to construct parametric images (maps) reflecting the spatial distribution of the rate of  $^{18}\text{F}$ -FLT cellular trapping (or proliferation). These estimates will be compared with kinetic parameters determined using traditional ROI-based pharmacokinetic modeling methods. As input to the model, venous time-activity curves will be derived non-invasively at the level of the confluence of the sagittal, straight, and transverse sinuses, and corrected for hematocrit and partial volume effects.

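### Secondary Aim #1 compares k3 only as ROI averages, so it can show that ROI means agree but does not support the Rationale's claim that voxel-wise estimation is validated

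*Combined protocol and SAP*

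**What the plan says.** Section 11.0 (Statistical Methodology for Secondary Aim #1) compares the k3 fitted to the whole ROI "to the average of the voxel-by-voxel parameter values among the voxels comprising the same ROIs". The stated wish, for each ROI, is for the k3 "value derived from the entire ROI to be within 25% of the average" over the voxels. The additional analysis is a CCC, adapted for clustered data, to "evaluate the agreement between the ROI-based and the average voxel-based parameter values". The aim itself is worded cautiously: "To attempt to corroborate voxel-based parameter estimates reflecting tumor cell proliferation with estimates derived using standard ROI-based pharmacokinetic modeling methods".

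Other sections describe the product at a finer scale. In section 4.2 (Secondary Aim #1 Study Design) the voxel estimates are "utilized to construct parametric images (maps) reflecting the spatial distribution of the rate of" FLT trapping. Section 3.6 (Rationale) speaks of laying the groundwork for interpreting FLT "heterogeneity within and across tumors on a voxel-wise basis" and then states: "The feasibility of voxel-wise estimation of proliferation will be established, and validated against traditional ROI-based pharmacokinetic approaches".

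On scale, section 4.2 (Primary Aim Study Design) says "ROIs will be no smaller than a cubic centimeter" and puts the accuracy of biopsy localization at about 1 cm³.

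**The concern.** A voxel-wise method is worth having only for what it shows below the level of the ROI; the standard ROI fit already gives the ROI mean. The planned comparison averages that added information away before testing anything. A map dominated by noise and a map that is right voxel by voxel can therefore give the same ratio and the same CCC.

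The protocol intends the results to inform larger prospective studies. If good ROI-mean agreement were reported as validation of the voxel maps, those studies could rely on fine spatial detail that had never been checked. Voxel noise is a reasonable worry here: section 3.4 fits five parameters (K1, k2, k3, k4 and Vb) in every voxel, and section 4.3 supplies 6 + 7 + 10 = 23 time frames.

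**Working it through.** **The plan's own figure.** The only planning figure tied to this aim is the CCC precision in section 11.0: 95% half-widths of 0.27, 0.20 and 0.05 at CCC 0.8, 0.9 and 0.99, with an average of two observations per patient. A bivariate normal simulation of 15 patients with two ROIs each, and an assumed within-patient correlation of 0 to 0.9, gave 0.14–0.21, 0.08–0.12 and 0.008–0.013. These are narrower, but the plan does not give its simulation model or interval method, so its figures can be neither reproduced nor called wrong. They concern the precision of agreement between ROI means and do not bear on this point.

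**Step 1: what the statistics depend on.** For ROI *i* with voxel values k3(i,1) … k3(i,m), let M(i) = (1/m) Σ k3(i,v), and let R(i) be the whole-ROI fit. The ratio is R(i)/M(i), and the CCC is a function of the pairs (R(i), M(i)). A mean does not depend on the order or spread of its terms, so any change to the voxel values that keeps M(i) leaves both statistics unchanged. This needs no assumption.

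**Step 2: illustration.** 30 simulated ROIs (15 patients × 2), with 64 voxels each (assumed):

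| Voxel map | ROIs within 25% | CCC | Mean within-ROI correlation with truth |
|---|---|---|---|
| Good map | 100% | 0.974 | +0.97 |
| Shuffled in ROI | 100% | 0.974 | +0.01 |
| Reflected about ROI mean | 100% | 0.974 | −0.97 |
| Flattened to ROI mean | 100% | 0.974 | about 0 |

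With 20 and 125 voxels the CCC was likewise identical across the four maps (0.966 and 0.984).

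**Step 3: noise rather than shuffling.** Assume 4 mm voxels, so 1000 mm³ / 64 mm³ ≈ 16 per 1 cm³, or 8 to 16 effective voxels after spatial correlation. Assume also unbiased voxel error and an error-free ROI fit. Then

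P(within 25%) = 2Φ(0.25 / (CV/√n)) − 1.

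| Voxel CV | n = 8 | n = 16 |
|---|---|---|
| 50% | 2Φ(1.41) − 1 = 0.84 | 2Φ(2.00) − 1 = 0.95 |
| 60% | 2Φ(1.18) − 1 = 0.76 | 2Φ(1.67) − 1 = 0.90 |
| 100% | 2Φ(0.71) − 1 = 0.52 | 2Φ(1.00) − 1 = 0.68 |

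If the true within-ROI CV were 30% (assumed) and the noise CV 50%, the real share of the visible voxel variance would be 0.09/(0.09 + 0.25) = 0.26, leaving about 0.74 as noise. Most ROIs would still meet the limit.

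**Step 4: where the unbiased-error assumption fails.** The voxel fit is nonlinear, so large noise shifts the mean. In a simulated five-parameter fit on the protocol's frame sequence, with assumed input curve, rate constants and noise and 16 independent voxels, 93–100% of ROIs met the limit at a voxel CV of about 0.5. At a CV of about 0.7–0.9 the median ratio fell to 0.71–0.84 and 40–63% met it. A separate simulation under other assumed settings gave 83–100% for CVs of 0.2–0.7. The test therefore has some sensitivity to heavy noise, but how much depends on the settings.

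**Step 5: the opposite error.** With noise-free and correct voxel values, and K1 and k3 varying together (assumed log-SD 0.6), the ratio averaged 1.23 (range 1.15–1.31). Some correct maps would miss the limit. With log-SD 0.3, or with K1 and k3 independent, it stayed within about 0.92–1.11.

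**Step 6: whether another analysis fills the gap.** Section 1.1 assigns the accuracy of the parametric images to comparison with histology at different biopsy locations. That comparison is made per biopsy site, at most four per patient, with ROIs of at least 1 cm³ and localization of about 1 cm³. It gives evidence between sites. It cannot resolve the pattern inside a minimum-size ROI.

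**The case against.** The strongest reply is that the plan promises little. The aim is an attempt at corroboration, the 25% figure is a wish, and section 11.0 calls all analyses purely exploratory with no rigorous hypothesis testing. The histology and gene-expression comparisons work per biopsy site, so ROI-mean agreement is the property that this study itself uses. All of this stands. It makes the point one about the conclusion drawn and a missing report, not about a failed design.

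Three stronger readings are tempting, and the documents do not support them.

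- *The study has no spatial check at all.* It has one between sites: up to four ROIs per patient, chosen for contrast in PET and MRI, are compared with tissue.
- *A noise map would be formally passed.* There is no pass/fail rule to trigger. The wish is stated for each ROI, and about 30 are expected. If ROIs were independent, the step 3 rates imply that all 30 meet the limit with probability 0.843^30 = 0.6% to 0.954^30 ≈ 25% at a CV of 50%.
- *Averaging always hides voxel noise.* Step 4 shows that heavy noise partly appears as bias in the ratio.

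What remains is the statement of validation in section 3.6, which goes further than the comparison in section 11.0 can.

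**Conclusion.** The concern holds in a limited form. The ratio and the CCC can show agreement of ROI means, including average fitting bias and coarse differences between ROIs. They do not describe the k3 pattern or noise inside an ROI, so the validation promised in section 3.6 does not follow from them. That part is algebraic and independent of sample size or noise.

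The size is conditional. At a voxel CV of about 50%, with 8–16 effective voxels, unbiased error and an error-free ROI fit, roughly 84–95% of ROIs would still fall within 25%. None of these inputs is in the documents, so the range shows what could happen and does not predict this trial.

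**What to change.** 1. In sections 3.6 and 11.0, state that the ratio and CCC analysis addresses ROI-mean agreement, and reword the claim of validation to match.
2. For each ROI, report from the existing voxel fits:
   - the robust CV of voxel k3;
   - the share of voxel fits that end at a parameter bound;
   - the observed within-ROI variance of voxel k3 next to the mean squared standard error of the voxel fits. The ratio of the second to the first estimates the share of visible variation that is noise.
3. Base any voxel-wise claim on item 2.

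One apparently natural addition should not serve as the validation: splitting each ROI into sub-blocks and correlating the sub-block ROI fit with the sub-block voxel mean. Both come from the same counts. In simulations with no true heterogeneity, that correlation was 0.76–0.98 under one set of assumptions and 0.64–0.99 under another, so a map of pure noise would look corroborated.

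The cost is a little extra analysis of existing fits, some rewording and a narrower stated conclusion. No new patients, scans or tissue are needed.

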## 11.0 BIOSTATISTICS

This is a pilot study intended to collect preliminary data on 15 patients diagnosed with untreated high-grade glioma who are scheduled to undergo surgical resection.

Primary Aim: To investigate relationships between voxel-based determinations of proliferation rate and observed MR imaging features, as well as with spatially registered histologic measures of tumor cell proliferation (Ki67) and microvascular density (CD31) at corresponding locations.

Statistical Methodology for Primary Aim: In this aim, we will first explore the relationships between  $^{18}\text{F}$ -FLT PET parameters and MR imaging features ( $K_{\text{trans}}$  or microvascular permeability). The  $^{18}\text{F}$ -FLT PET parameters:  $K_1$  (tracer delivery rate constant),  $k_2$  (rate constant reflecting flow from the tumor interstitial compartment back to blood),  $k_3$  (rate constant reflecting proliferation), and  $k_4$  (rate constant reflecting flow from tumor cells back into the tumor interstitial space) will be compared to  $K_{\text{trans}}$  on MR imaging. We will also explore relationships between  $K_{\text{trans}}$ , each of the  $^{18}\text{F}$ -FLT PET parameters, and the histological markers Ki67 and CD31. All of the parameters and markers are measured on a continuous scale. Initially graphical methods such as pair-wise scatter plots will be used to assess the relationships. The relationships between each pair of variables will be more formally evaluated using methods that account for correlated data (there may be up to four observations per patient) such as random effects regression models or generalized estimating equations.

It is unlikely but possible that it may be determined at surgery that a patient does not have a high-grade glioma but instead has a metastasis or PCNSL. The likelihood that this will occur will be infrequent, if at all, given the constellation of distinctive imaging features that generally serve to differentiate these tumor types. If it does occur, however, we will continue accrual until 15 high grade glioma patients have been enrolled. In this case, two sets of analysis for the primary aim and all other aims will occur, one including all enrolled patients and one including only patients with high-grade gliomas. Patients found to have a metastasis or PCNSL may not yield different values than patients with glioma so the decision to include them in the analysis may not be unreasonable.

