All analyses are purely exploratory and intended to generate data for future studies. We do not plan to conduct any rigorous hypothesis testing. To explore what we might be able to say using this limited sample size, we find that with data on 15 patients we expect to be able to detect a moderately high correlation coefficient of 0.60 with 80% power using a two-sided 0.05 level test. This calculation assumes that each patient contributes only one observation, but in our case, we expect an average of two observations for each patient (up to four samples per patient) which may increase our power to draw any conclusions. Simulation studies assuming an average of two observations per patient indicate that we can estimate the concordance correlation coefficient to within (half-width of 95% confidence interval)  $\pm 0.27$  for a CCC equal to 0.8,  $\pm 0.20$  for a CCC equal to 0.9, and  $\pm 0.05$  for a CCC equal to 0.99.

**Memorial Sloan-Kettering Cancer Center  
IRB Protocol**

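### Secondary Aim #1 reads each ROI's k3 ratio only as inside or outside 25% and names no summary of its offset, scatter or clustering

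*Combined protocol and SAP*

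**What the plan says.** In Section 11.0, Statistical Methodology for Secondary Aim #1, each ROI yields two k3 values: one fitted to the whole ROI, and the average of the voxel-by-voxel fits within it. The plan states: "For each ROI, we would like to see the estimated $k_3$ value derived from the entire ROI to be within 25% of the average" of the voxel values. It adds: "The ratio of two $k_3$ values will be computed for this purpose".

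A supplementary measure, on the uncut k3 values, comes next in the plan: "we will calculate the concordance correlation coefficient (CCC) to evaluate the agreement between the ROI-based and the average voxel-based parameter values". Clustering is addressed there: "A modified version of the CCC that allows for clustered data" is to be used. Nothing similar is said about the ratio.

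Section 11.0 describes a pilot of 15 patients. Its sample size justification says "we expect an average of two observations for each patient (up to four samples per patient"), which makes about 30 ROIs and at most 60. The same section calls all analyses exploratory and disclaims rigorous hypothesis testing. It gives an expected precision for the CCC, but no figure for the 25% target: no SD of the ratio, no expected share within the band, and no required number.

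**The concern.** The ratio is a continuous measure, but the only stated use of it is to see on which side of 25% each ROI falls. On that reading 1.24 counts the same as 1.00, and 1.26 the same as 3. The plan does not say how the results from about 30 ROIs become one statement about agreement.

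Section 3.6 presents the study as validating voxel-wise estimation against the ROI-based approach and as informing larger studies. Designers of those studies need two separate quantities: whether one method reads consistently higher (a calibration matter) and how far single ROIs scatter (noise). The in/out reading supplies neither.

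**Working it through.** **The plan's own figures.** The only figures for this aim are the 95% CI half-widths of the CCC: ±0.27, ±0.20 and ±0.05 at CCC 0.8, 0.9 and 0.99. Simulating 15 patients and 30 ROIs under several models gave about 0.14–0.30, 0.08–0.18 and 0.01–0.02. The plan does not state its simulation model, so these figures are neither confirmed nor disputed. They do not bear on the 25% target.

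**Inputs.** 15 patients × 2 ROIs = 30 ROIs (Section 11.0). The band is 0.75 to 1.25. Assumptions: log ratios are normal with no offset, and their SD s is shown over a range.

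**1. Read as every ROI.** The chance that one ROI passes is p = Φ(ln 1.25 / s) − Φ(ln 0.75 / s), with ln 1.25 = 0.223 and ln 0.75 = −0.288. For independent ROIs, all 30 pass with probability p^30.

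| s | p | all 30 pass |
|---|---|---|
| 0.08 | 0.997 | 0.92 |
| 0.10 | 0.985 | 0.64 |
| 0.12 | 0.960 | 0.30 |
| 0.15 | 0.904 | 0.05 |
| 0.20 | 0.793 | 0.001 |

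The probability crosses one half at s ≈ 0.108. A within-patient correlation of 0.5 changes little: 0.66, 0.33 and 0.06 at s = 0.10, 0.12 and 0.15. The result also depends on the number of ROIs. At s = 0.10, doubling to 60 ROIs gives 0.64² ≈ 0.41 with the agreement unchanged.

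**2. Read as a share.** Exact 95% CIs, treating ROIs as independent:
- 24/30: 0.61 to 0.92
- 27/30: 0.73 to 0.98
- 30/30: 0.88 to 1.00 (lower limit 0.025^(1/30) = 0.884)

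With two ROIs per patient the effective number is 30/(1 + ICC), which is 20 at ICC 0.5 and 15 at ICC 1. At 15, a result of 13/15 has CI 0.60 to 0.98.

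**3. Offset against scatter.** Two quite different situations give almost the same share:
- No offset, s = 0.197: Φ(1.13) − Φ(−1.46) ≈ 0.80.
- A steady ratio of 1.20, s = 0.05: the upper limit is (0.223 − 0.182)/0.05 = 0.82 SDs away and the lower limit is remote, so Φ(0.82) ≈ 0.79.

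The first is noise and the second a calibration difference.

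**4. Does the CCC fill the gap?** On the log scale, with no offset, equal error in the two methods and between-ROI SD B, CCC = B²/(B² + s²/2). Hold s at 0.15, so s²/2 = 0.01125:
- B = 0.1: 0.01/0.02125 = 0.47
- B = 0.3: 0.09/0.10125 = 0.89
- B = 0.8: 0.64/0.65125 = 0.98

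The same disagreement relative to 25% gives very different CCCs, so the CCC cannot be read against that tolerance.

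**5. What the continuous ratio would give.** The 95% CI of the geometric mean ratio is exp(±t·s/√n), shown here for an effective n of 30 down to 15. The 95% limits of agreement are exp(±1.96s).

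| s | CI factor (× or ÷) | limits of agreement |
|---|---|---|
| 0.10 | 1.04–1.06 | 0.82–1.22 |
| 0.15 | 1.06–1.09 | 0.75–1.34 |
| 0.20 | 1.08–1.12 | 0.68–1.48 |

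Offset would thus be estimated quite closely even in this small sample, and scatter would be reported separately.

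**The case against.** The strongest reply is that the plan contains no rule to fail. Its wording expresses a wish. No all-ROI requirement, count of passes or consequence of a miss is written, and the section disclaims rigorous testing. This stands, and it rules out three stronger readings that a reader might infer.

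- **That sound methods will usually miss the target.** This needs an SD that the documents do not give. Below about 0.108 it reverses: all 30 ROIs pass with probability 0.64 at 0.10 and 0.92 at 0.08.
- **That a count out of 30 is uninformative.** It is imprecise. Requiring at least 26 of 30 has one-sided error 0.030 at a true share of 0.70 and power 0.82 at 0.90, if ROIs are independent. It cannot usefully separate 0.90 from 0.95: requiring 30 of 30 has power 0.95^30 = 0.21.
- **That the continuous information is thrown away.** The ratio is computed for every ROI, and the clustered CCC uses uncut k3 values and penalises both shift and scatter. What is missing is a named summary of the ratio.

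The absence of a source for 25% is not a fault in itself, since a pilot may set a working tolerance.

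The reply does not remove the gap. A study meant to generate data for later ones has most use for estimates of offset and scatter, and those are what the plan leaves unspecified.

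**Conclusion.** The point holds as a gap in specification and reporting for an exploratory secondary aim. The lead analysis reads the ratio only against a 25% band, with no summary of offset or scatter, no rule for combining ROIs and no adjustment for clustering. The CCC does not replace these.

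How often an every-ROI target would be missed depends on the assumed log-ratio SD: at 30 ROIs, all pass with probability from 0.92 (SD 0.08) to 0.05 (SD 0.15), given normal log ratios and no offset. Two conclusions do not depend on that SD. An interval for a share out of about 30 is wide, and a share cannot distinguish offset from scatter. The documents do not support saying that the aim is bound to fail or that its results would be worthless.

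**What to change.** In Section 11.0, Secondary Aim #1, make the lead summary an analysis of log(ROI k3 / mean voxel k3) with a random patient intercept. Report:

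- the geometric mean ratio with 95% CI (offset);
- the 95% limits of agreement with their CIs (scatter);
- both beside the plan's band of 0.75 to 1.25, as estimates.

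Do not require that the limits of agreement, or every ROI, fall inside the band. Such a rule would bring back the same difficulty. At s = 0.12, where 96% of ROIs pass, the upper limit is exp(1.96 × 0.12) = 1.27, already outside. In a simulation of 30 independent ROIs against the slightly narrower band 0.80 to 1.25, with a true 95% of ROIs inside it, the estimated limits fell within that band in only 33% of studies.

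Keep the share of ROIs within 25% as a descriptive line and the clustered CCC as the additional analysis.

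The cost is a few sentences in the plan and a few lines of code on ratios already to be computed, with no new patients, scans or readings. The small downside is an approximate log-normal assumption, which a plot of the ratios can check.

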## 2.0 OBJECTIVES AND SCIENTIFIC AIMS

Primary Aim: To investigate relationships between voxel-based determinations of proliferation rate and observed MR imaging features (i.e.,  $K_{trans}$  or microvascular permeability; fBV, tissue fractional blood volume), as well as with spatially registered histologic measures of tumor cell proliferation (Ki67) and microvascular density (CD31) at corresponding locations.

Secondary Aim #1: To attempt to corroborate voxel-based parameter estimates reflecting tumor cell proliferation with estimates derived using standard ROI-based pharmacokinetic modeling methods, for improving the characterization of high-grade gliomas using dynamic  $^{18}\text{F}$ -FLT PET-CT.

Secondary Aim #2: To assess whether static measures of  $^{18}\text{F}$ -FLT uptake can adequately serve as non-invasive biomarkers of proliferative activity or whether parametric images, based on compartmental analyses of the FLT pharmacokinetics, are required by correlating findings of both approaches with regional histologic assays of tumor cell proliferation.

Exploratory Aim: To evaluate whether differences in gene expression seen between areas of increased and decreased proliferative activity on parametric maps define consistent differential transcriptome signatures for comparison with known molecular subclasses of GBM and known pathways.

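### Secondary Aim #2 asks whether SUV is adequate or k3 images are required, but plans no interval for the difference between the two markers

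*Combined protocol and SAP*

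**What the plan says.** Section 2.0 and Section 11.0 both pose the question as a choice. Section 11.0 asks whether static measures "can adequately serve as non-invasive biomarkers of proliferative activity or whether parametric images, based on compartmental analyses of the FLT pharmacokinetics, are required".

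For the analysis, Section 11.0 carries over the primary-aim methods. Each pair of variables is examined by scatter plot and then by a method that allows for several sites per patient, "such as random effects regression models or generalized estimating equations". SUV and k3 are each related to Ki67 in this way. The step from two relationships to an answer is one sentence: "The strength of the relationship between these two parameters and Ki67 will be compared descriptively".

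Section 4.2 (Secondary Aim #2 Study Design) shows that both markers are read at the ROIs chosen for biopsy and set against the MIB-1 percentage, so the data are paired by specimen.

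The sample size justification in Section 11.0 gives precision for a single correlation and, for Secondary Aim #1, 95% half-widths for the concordance correlation coefficient. It gives nothing for the SUV-k3 difference. It also states that every analysis is exploratory and that no rigorous testing is planned.

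**The concern.** The aim is a head-to-head question about two markers measured on the same tissue. Two separate models can give a standard error for each relationship with Ki67. They do not give the uncertainty of the difference, because that depends on how strongly SUV and k3 are correlated with each other. Without that uncertainty, the reader cannot tell an informative gap from one that sampling alone would produce.

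Section 3.3 says there is no consensus between static and dynamic measures, and Section 3.6 says the results may inform larger studies. The interval would let those designers see how much, or how little, this pilot says about the choice.

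The index of strength is also left open. Section 4.2 speaks of correlating, while Section 11.0 points to regression or estimating equations. Regression slopes for SUV and for k3 are on different scales and cannot be compared directly.

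**Working it through.** **Inputs from the documents.** 15 patients; on average two sites per patient, at most four (Section 11.0, sample size justification). That is about 15 × 2 = 30 clustered observations.

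**Assumptions, because the documents give no values.** Intraclass correlation 0.3 to 0.5; SUV-k3 correlation 0.3 to 0.9; true correlations with Ki67 as stated below.

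**1. The plan's own figure.** The plan says 15 patients can "detect a moderately high correlation coefficient of 0.60 with 80% power using a two-sided 0.05 level test", and adds: "This calculation assumes that each patient contributes only one observation". With Fisher's z, power = Φ(atanh(r)·√(n−3) − z).
- atanh(0.60) = 0.693 and √12 = 3.464; the product is 2.401.
- Two-sided: Φ(2.401 − 1.960) = Φ(0.441) = 67% (about 70% with bias correction or by simulation).
- One-sided: Φ(2.401 − 1.645) = Φ(0.756) = 77.5% (about 80% with bias correction).

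So 80% is matched only by a one-sided test. This is a side finding. In any case the figure concerns one correlation against zero, not a difference between two.

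**2. Chance gap between equal markers, by formula.** Let both true correlations with Ki67 be ρ = 0.5, let c be the SUV-k3 correlation, and let d be the k3 correlation minus the SUV correlation. In large samples

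n·Var(d) = 2[(1−ρ²)² − ψ], with ψ = c(1−2ρ²) − ½ρ²(1−2ρ²−c²).

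For c = 0.6: ψ = 0.300 − 0.125 × 0.14 = 0.2825, so n·Var(d) = 2(0.5625 − 0.2825) = 0.56. The SD of d is √(0.56/15) = 0.193 if sites within a patient add nothing (n = 15), and √(0.56/30) = 0.137 if they are independent (n = 30). Then P(|d| > 0.2) = 30% and 14%. The same steps give 42% and 26% at c = 0.3, 15% and 4% at c = 0.8, and 4% and 0.4% at c = 0.9. The clustered design should fall between each pair.

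**3. The same quantity by simulation.** For each site, Ki67, SUV and k3 were drawn as trivariate normal, as a patient part plus a site part with variance shares ICC and 1−ICC. There were 15 patients with a mean of two sites.

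| SUV-k3 correlation | Equal markers (0.5, 0.5): observed gap > 0.2 | k3 better (0.6 v 0.5): SUV looks better |
|---|---|---|
| 0.3 | 29-34% | about 30% |
| 0.6 | 18-21% | 24-26% |
| 0.8 | 7-9% | 17-18% |
| 0.9 | 1-3% | 9-10% |

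Ranges cover ICC 0.3 to 0.5; repeat runs agreed to about one percentage point. The first column lies inside the bounds from step 2 throughout. At 0.6, gaps above 0.1 occur in 49-52% of trials.

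**4. What the interval would look like.** For true correlations of 0.6 (k3) and 0.4 (SUV), a percentile bootstrap that resamples patients gives a 95% interval with half-width about 0.28. Its actual coverage was about 91-92%, with separate runs between 89% and 93%. It excluded zero in about a third of trials (27-36%).

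**The case against.** The strongest reply is that the plan claims very little. It calls itself a pilot, declares all analyses exploratory and disclaims rigorous testing. A descriptive comparison fits that status, and nothing forbids showing intervals. This stands, and it is why the point is an improvement and not an error.

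Three stronger readings are tempting, and the documents do not support them.
- A reader might infer that chance will decide the answer, because the marker with the larger correlation will be preferred. No rule in the plan picks a marker that way, and Section 3.6 says only that results may inform later work.
- A reader might infer that uncertainty is ignored altogether. The clustered models would normally give a standard error for each marker; only the paired difference is uncovered.
- A reader might infer that the ranking will usually mislead. That depends on an undocumented correlation. At 0.9, chance gaps above 0.2 almost vanish. The wrong ranking in about a quarter of trials (at 0.6) refers to a true gap of only 0.1, where a mistake costs least.

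It is also fair to say that the interval would seldom settle the question, and that no interval for a difference can show SUV to be adequate. Both markers could be equally poor, and adequacy needs a margin that the plan does not state. These points limit what the interval can be used to claim. They do not remove the reason to report it, since exploratory status rules out a test, not an estimate with its precision. The plan already takes that approach for the concordance coefficient.

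**Conclusion.** The point holds as a modest, inexpensive improvement to a secondary aim. The either/or wording of the aim is stronger than a descriptive comparison can support, and the plan does not provide the one quantity that would show how much the data say: an interval for the paired difference.

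The size depends on the assumed SUV-k3 correlation. Equal markers would look more than 0.2 apart in about a third of trials at 0.3, about a fifth at 0.6, and 1-3% at 0.9. These figures also rest on normal data, 15 patients with a mean of two sites, and an intraclass correlation of 0.3 to 0.5. The paired interval reflects the SUV-k3 correlation actually observed, so it would show which of these situations applies. The finding does not call the design invalid or ask for more patients.

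**What to change.** In Section 11.0, Statistical Methodology for Secondary Aim #2:
1. Name one scale-free index of association, for example the correlation of each marker with Ki67 on the same specimens.
2. Report k3 minus SUV on that index with a 95% interval from a bootstrap that resamples patients. Label it approximate, because with 15 clusters the simple percentile version covers about 91-92%.
3. State that neither marker will be called superior unless the interval excludes zero, and that an interval including zero does not show SUV to be adequate.
4. In Sections 2.0 and 11.0, reword the aim from adequate-or-required to estimating the difference in association with Ki67.

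The cost is a little extra analysis on data already being collected. The downside is a less decisive report: even at a true difference of 0.2, about two thirds of such intervals would include zero.
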